## 15.0 CLINICAL TRIAL WITHDRAWALS/ DROP-OUTS

Patients may be withdrawn from the study at their own request or at the discretion of the Investigator for one of the following reasons:

- Patient withdraws consent to participate.
- Pregnant female patients must be withdrawn from the study without delay. Follow-up should be performed in accordance with [Section 17.10](#).
- Patient has an AE that, in the opinion of the Investigator, requires the patient's discontinuation. Follow-up should be in accordance with [Section 17.9](#).
- Any clinically significant abnormal findings in physical examination, ECG, vital signs, haematology, chemical chemistry which, in the opinion of the Investigator may compromise the safety of the patient in the study or interfere with evaluation of the IMP or reduce the patient's ability to participate in the study.
- Intercurrent illness requiring pharmacological treatment with a non-permitted drug or a drug which interacts in any way with the test treatment or with study evaluations.
- Patient is non-compliant with the protocol.
- Continuation in the study would be detrimental to the patient's safety in the opinion of the Investigator.
- The Investigator or the Sponsor, for any reason, stops the study.
- Sponsor, CA, or EC terminate the trial at an individual site.

Patients who prematurely withdraw from the study while receiving study medication should complete the EOT Visit assessments, when possible. Patients must return the medications and details regarding AEs and concomitant medications will be collected.

Patients who are withdrawn from the study will not be replaced. In the event that a patient discontinues from the study prematurely due to an AE or SAE, they will be followed until the event has resolved (returns to normal or baseline values) or has stabilised.

The reason for withdrawal of a patient from the study or premature discontinuation of the treatment must be fully documented in the eCRF as well in source documents. Follow-up for withdrawn patients follows the procedures described in [Section 17.8](#) and [Section 17.9](#).

## **16.0 STOPPING AND DISCONTINUATION CRITERIA FOR THE TRIAL**

The study may be prematurely terminated for one of the following reasons:

- The Sponsor feels that the number and/or severity of AEs justify discontinuation of the study.
- The Sponsor considers the applied doses of the IMP to no longer be relevant.
- Data not previously known become available and raise concern about the safety of the IMP so that continuation would pose potential risks to the patients.
- Difficulties in enrolment that would compromise reasonable timing for study conclusion or would delay study beyond reasonable timing and results.

Premature termination of the study must be reported to the EC and CA according to applicable laws generally within 15 days. A detailed written explanation of the reason should be given and alternative procedures for patients under treatment specified. However, study results have to be reported according to the requirements outlined in this protocol as far as applicable.

If after the termination of the trial, the risk/benefit analyses have changed, the new evaluation should be provided for the best interest of the patients who have participated in the study.

The Sponsor reserves the right to discontinue the study at a particular site or at multiple sites for safety or administrative reasons at any time. Should the study be terminated and/or the site closed for whatever reason, all documentation and investigational product pertaining to the study must be returned to the sponsor or its representative.

## **17.0 REPORTING SAFETY INFORMATION**

### **17.1 Definition of Adverse Event (AE)**

An Adverse Event (AE) is "*any untoward medical occurrence in a patient or clinical trial subject administered a medicinal product and which does not necessarily have a causal relationship with this treatment*".

Adverse events include:

- Worsening (change in nature, severity or frequency) of conditions present at the onset of the study.
- Patient deterioration due to the primary illness.

- Intercurrent illnesses.
- Drug interactions.
- Events related or possibly related to concomitant medications.
- Abnormal laboratory values, as well as significant shifts from baseline within the range of normal, which the Investigator considers to be clinically significant.

An AE can therefore be any unfavourable and unintended sign (including an abnormal laboratory finding), symptom, or disease temporally associated with the use of an IMP, whether or not considered related to the IMP.

The following medical conditions will not be documented as AEs and will be documented as medical history (or other as applicable):

- Symptoms or laboratory or instrumental abnormalities of a pre-existing (i.e. before patient entered the study) condition which have not worsened since enrolment;
- Surgical interventions or hospitalizations planned before patient entered the study.

## 17.2 Definition of Adverse Event of special interest

No AEs of special interest are defined for this trial.

## 17.3 Definition of Adverse Drug Reaction (ADR)

An Adverse Drug Reaction (ADR) is “any untoward and unintended response to an IMP related to any dose administered and which implies an AE with at least a reasonable possibility of a causal relationship with the use of the product (i.e. a causal relationship cannot be ruled out, meaning that there is evidence or arguments to suggest a causal relationship). The definition covers also medication error and uses outside what is foreseen in the protocol, including misuse and abuse of the IMP ”.

All AEs judged by either the reporting Investigator or the Sponsor as having a reasonable causal relationship to a medicinal product qualify as ADRs.

### 17.3.1 Definition of Unexpected Adverse Drug Reaction

An unexpected ADR is “an adverse reaction, the nature, or severity of which is not consistent with the applicable product information (e.g., Investigator's Brochure [IB] for an unapproved investigational product or Summary of Product Characteristics [SmPC], for approved product) ”.

The Reference Safety Information for evaluation of AE expectedness in this trial will be the IB (13).

## 17.4 Definition of Serious Adverse Events or Serious Adverse Drug Reaction

A Serious Adverse Event (SAE) or Serious Adverse Reaction (SAR) is: “any untoward medical occurrence or effect that at any dose ”.

- Results in death.

- Is life-threatening (i.e. the patient was at risk of death at the time of the event/reaction; it does not refer to an event/reaction which hypothetically might have caused death if it were more severe).
- Requires inpatient hospitalisation or prolongation of existing hospitalisation.
- Results in persistent or significant disability/incapacity (where disability is defined as a permanent or substantial disruption of ability to carry out normal life functions, either reported or defined as per clinical judgement).
- Is a congenital anomaly/birth defect.
- Is an important medical event that may not result in death, be life-threatening, or require hospitalisation but, according to appropriate medical judgment, it may jeopardise the patient and may require medical or surgical intervention to prevent any of the outcomes listed in the definition above. Examples of such events include allergic bronchospasm requiring intensive treatment in an emergency room or at home, and blood dyscrasias or convulsions that do not result in hospitalisation, or development of drug dependency or drug abuse.

Any suspected transmission via a medicinal product of an infectious agent is also considered an SAE.

A non-serious adverse event (non-SAE) is any AE that does not meet the criteria listed above for an SAE.

#### ***17.4.1 Definition of Suspected Unexpected Serious Adverse Reactions***

A SUSAR (Suspected, Unexpected Serious Adverse Reaction) is a subset of SAEs/SARs that, although foreseeable, are potentially related to the IMP and not identified in the reference safety information and will be reported to the appropriate regulatory authorities and investigators following local and global guidelines and requirements.

### **17.5 Definition of Severity of Adverse Events**

The term “severe” is used to describe the intensity (severity) of a specific event:

- Mild: causing no limitation of usual activities; the patient may experience slight discomfort.
- Moderate: causing some limitation of usual activities; the patient may experience annoying discomfort.
- Severe: causing inability to carry out usual activities; the patient may experience intolerable discomfort or pain.

### **17.6 Definition of Adverse Event Causality**

Causality shall be determined according to the definition of ADR as given in [Section 17.3](#).

All AEs judged by either the Investigator or the Sponsor as having a reasonable suspected causal relationship to an IMP qualify as ADRs. The causality assessment given by the Investigator should not be downgraded by the Sponsor.

The following binary decision for causality will be used:

- Reasonable possibility that the IMP caused the event.

- No reasonable possibility that the IMP caused the event.

Features supportive of an association include:

- Temporal plausibility.
- Pharmacological properties of the drug or of the substance class.
- Course of the AE after dechallenge and, if applicable, after rechallenge.
- Specific tests indicating involvement of the drug in the occurrence/worsening of the AE.
- Alternative explanations.

## 17.7 Adverse Event Recording

Each AE occurring to a patient, either spontaneously revealed by the patient or observed by the Investigator, whether believed by the Investigator to be related or unrelated to the IMP, must be recorded on the AE information page of the eCRF. Also for SAEs, information must be recorded in the eCRF ([Section 19.1](#)).

The Investigator performs an evaluation with respect to seriousness and causality of the AEs and records it on the appropriate section of the eCRF.

## 17.8 Adverse Event Reporting

The Investigator must report to the CRO all AEs which occur during the study following written informed consent, regardless of their relationship to IMP. All AEs are to be recorded by the Investigator on the AE information page of the eCRF. For SAEs information must be recorded also on the "Adverse Event Form for immediate reporting".

In addition, an SAE will have to be reported according to the following detailed procedure.

### 17.8.1 Reporting Serious Adverse Events

Investigators must report SAEs **within 24 hours of first awareness of the event**.

The SAE must be reported through the eCRF to the CRO's Pharmacovigilance group as per contact details provided in the "List of Zambon/CRO personnel" at the beginning of this CTP.

If there is any issue with the electronic reporting process, such as internet failure or database issues, this must not delay SAE reporting. The back-up procedure is to send the back-up paper Serious Adverse Event Form to the CRO's Pharmacovigilance group by email or fax using the contact details specified in the SAE guidelines and SAE report form.

Note: Any reports submitted on paper must be retrospectively added to the eCRF as soon as possible.

The national and local standards of confidentiality must always be maintained and any relevant national legislation on data protection must be followed.

SAEs are reportable from the time a patient signs the informed consent to the follow-up phone call or visit occurring 2 weeks ( $\pm$  3 days) after the last dose of IMP.

If the Investigator becomes aware of any SAE occurring to a subject within the follow-up window established in this CTP, he/she will report the SAE as above. The SAE will be also reported in the eCRF.

If the Investigator becomes aware of any SAE outside the follow-up window established in this CTP, it is the Investigator's responsibility to report the SAE to the CRO. The Investigator might use the eCRF, as described above. However, the SAE is not an event occurred within the trial period.

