#### Treatment Period

At baseline (day 1), eligible patients will enter the treatment period and will be randomised to receive either safinamide (initial 50 mg titrated to 100 mg the day after the Visit 3/week 2, ideally at day 15) or matching placebo, orally od in a 1:1 ratio. The investigational medicinal

product (IMP) will be taken in the morning at breakfast time, in addition to the morning dose of L-dopa and other (if any) PD medications.

Following completion of all baseline assessments, they will receive the first dose of safinamide or placebo (50 mg) at the study centre. The day after the Visit 3/week 2 (ideally at day 15) the dose will be increased at home to 100 mg od. Each patient will receive treatment for 16 weeks, with visits at week 0/day 1 (baseline) and at weeks 2, 6, 10 and 16 (or early termination). A telephone follow-up will be performed 1 week after the end of treatment for safety reasons.

Patients who prematurely withdraw from the study while receiving study medication should complete the early termination visit assessments, when possible.

At the end of the study, the patients will be instructed to contact immediately the Investigator in case of appearance of any adverse reactions. Any ongoing adverse event or clinically abnormal laboratory parameter will be followed until resolution. In addition, all SAEs occurring within 30 days after a patient's last dose of study drug will be followed to their conclusion.

*In the case of intolerable dopaminergic adverse events (AEs), e.g. dyskinesia, it is suggested to decrease the dose of L-dopa by a telephone call as a first step and consider the decrease of the dose of safinamide or placebo from 100 to 50 mg od as a second step. In this second case, patients should undergo an unscheduled visit for safety reasons and maintain the 50 mg dose for the rest of the study. Patients who do not tolerate the 50 mg dose should withdraw from the study and complete the early termination visit assessments, when possible.*

**Efficacy** will be assessed by the changes in "OFF" and "ON" time from the 24-hour patient diary, the Unified Parkinson's Disease Rating Scale (UPDRS), the Clinical Global Impression (CGI), the Parkinson's Disease Questionnaire-39 items (PDQ-39) and the Numerical Rating Scale (NRS).

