## 7.2 Duration of Clinical Trial

Study participation will be up to a maximum duration of 18 weeks and will comprise a screening period (up to 2 weeks), a treatment period (16 weeks) and a 1-week telephone follow-up.

The start of the study is defined as the date of the first visit of the first patient participating in the study.

The end of the study is defined as the date of the last visit of the last patient participating in the study.

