### **9.3 Telephone Follow-up**

A telephone follow-up call will be performed 1 week after the end of treatment for safety reasons. The following assessments and procedures will be performed as detailed in the Study Flow Chart ([Section 29.0, Appendix 1](#)):

- Recording of concomitant medications and therapies.
- Recording of AEs.

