### 10.1.7 Safety Evaluations

Safety will be assessed throughout the study, i.e. from the provision of informed consent until the last patient visit. In addition, any AE that, in the opinion of the Investigator, requires the patient to withdraw from treatment or from the study, will be followed until the event has subsided or the condition has stabilised. All SAEs that are spontaneously reported within 30 days of a patient's last dose of study drug will also be reported and followed.

Individual safety assessments will be performed using the parameters and time points for collection listed below:

- Physical examination, clinical chemistry and haematology and 12-lead ECG at screening (visit 1) and week 16 (visit 6/EOT/ET).
- Neurological examination at screening (visit 1).
- Vital signs at each study visit AEs at every post-screening visit.

Further details are provided in [Section 10.1](#) and in the Study Flow Chart ([Section 29.0, Appendix 1](#)).

Further information regarding AE definitions and reporting is provided in [Section 17.0](#).

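### Section 17.8.1 ends SAE reporting at a contact 2 weeks after the last dose that is not scheduled, and leaves the eCRF recording of SAEs on days 15 to 30 optional although two other sections work to 30 days

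*Protocol*

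**What the plan says.** On the end of reporting, Section 17.8.1 says: "SAEs are reportable from the time a patient signs the informed consent to the follow-up phone call or visit occurring 2 weeks", with a tolerance of 3 days either way, counted from the last dose.

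On the schedule, Section 7.1 (Treatment Period) says: "A telephone follow-up will be performed 1 week after the end of treatment for safety reasons". Section 9.3 repeats it: "A telephone follow-up call will be performed 1 week after the end of treatment for safety reasons". Section 7.2 lists "a treatment period (16 weeks) and a 1-week telephone follow-up". The flow chart in Appendix 1 puts this call at Day 119 ±3, with end of treatment at Day 112 ±3, and shows no later contact.

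On 30 days, Section 7.1 says that "all SAEs occurring within 30 days after a patient's last dose of study drug will be followed to their conclusion". Section 10.1.7 says: "All SAEs that are spontaneously reported within 30 days of a patient's last dose of study drug will also be reported and followed".

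On late events, Section 17.8.1 separates SAEs inside and "outside the follow-up window established in this CTP". Inside, the SAE is reported and entered in the eCRF. Outside, the investigator still has the "responsibility to report the SAE to the CRO", but use of the eCRF becomes optional and the event is stated not to belong to the trial period.

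**The concern.** Section 17.8.1 is the operative rule a site follows when an SAE occurs after treatment, and it fixes the end of reportability by a contact that the schedule does not contain. A site cannot carry out the rule as written: it makes one call, at about 1 week, and has no visit or call at 2 weeks.

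The same section uses its window to decide whether an SAE must be entered in the eCRF. Two other sections tell the site to report or follow SAEs up to 30 days. A site working to 30 days would naturally enter a day-20 SAE in the eCRF; a site working from Section 17.8.1 may stop at the CRO report. What is at stake is whether like events are recorded alike in the trial database, and whether the end of SAE collection can be stated in one sentence in the study report.

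**Working it through.** No power or alpha figure is involved. The check is day arithmetic on the flow chart, followed by a comparison of the sections.

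**Inputs**
- End of treatment visit: Day 112 ±3 (Appendix 1).
- Telephone call: Day 119 ±3 (Appendix 1).
- Contact named in Section 17.8.1: 14 ±3 days after the last dose.
- SAE period in Sections 7.1 and 10.1.7: 30 days after the last dose.

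**Step 1. Can the 2-week contact be reproduced from the schedule?**
- Nominal gap: 119 − 112 = 7 days, not 14.
- Last dose on Day 112, call window ±3: 7 − 3 = 4 to 7 + 3 = 10 days.
- Section 17.8.1: 14 − 3 = 11 to 14 + 3 = 17 days.
- Since 10 < 11, the ranges do not overlap.

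**Step 2. Does using both visit windows rescue it?**
- Shortest gap: 116 − 115 = 1 day. Longest gap: 122 − 109 = 13 days.
- Day pairs with a gap of at least 11 days: Visit 6 on Day 109 with the call on Day 120, 121 or 122 (3 pairs); Day 110 with 121 or 122 (2); Day 111 with 122 (1). That is 6 of 7 × 7 = 49.
- All six need an early Visit 6 and a late call, and none matches a call meant to fall 1 week after treatment.

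The 2-week contact is therefore not the scheduled call under another name.

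**Step 3. Which days are affected?**
- Days 8 to 14: reportable under Section 17.8.1, with no scheduled contact after the nominal call. 14 − 7 = 7 days.
- Days 15 to 30: inside the 30 days of Sections 7.1 and 10.1.7, outside the 2 weeks of Section 17.8.1. 30 − 14 = 16 days. With the ±3-day tolerance, 30 − 17 = 13 to 30 − 11 = 19 days.

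**Step 4. What must a site do with an SAE on day 20 that is spontaneously reported the same day?**

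| Question | 7.1 | 10.1.7 | 17.8.1 (2-week limit) |
|---|---|---|---|
| Report it? | silent | yes | yes, to the CRO |
| Follow it? | yes | yes | silent |
| Enter it in the eCRF? | silent | silent | optional |
| Part of the trial period? | silent | silent | no |

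Reporting and follow-up can be met under all three sections. eCRF entry and trial status are settled only by Section 17.8.1, and there in a way that sits badly with a 30-day reporting and follow-up period.

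**The case against.** The best defence is that the text can be followed. The sentence just before the references to the follow-up window gives 2 weeks, which is its natural meaning. Section 7.1 concerns following SAEs through, and Section 10.1.7 adds spontaneous reports to routine collection. Neither contradicts Section 17.8.1. Every SAE the investigator learns of goes to the CRO. By day 7 most drug has gone: with the 20 to 24 hour half-life in Section 4.2.1, 168/24 = 7 to 168/20 = 8.4 half-lives have passed.

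Most of this stands, and it limits the point. It does not supply the missing contact, and it leaves eCRF entry to choice on days 15 to 30.

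A reader might infer more than the documents support:
- That the window could end at day 7, with the 1-week call. Section 17.8.1 itself says 2 weeks, so the arguable range starts after that.
- That optional eCRF entry conflicts with Sections 17.7 and 17.9. Section 17.7 is a general recording rule to which Section 17.8.1 can be read as the specific exception. Section 17.9 concerns follow-up information only and refers back to Section 17.8.1.
- That late SAEs will be lost from the summary tables. Section 20.4.8 gives no end date for treatment-emergent events, but the SAP may set one, and Section 17.8.1 already declares such events outside the trial period.

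A fair challenge to the remedy is that a 30-day window lengthens the time without a scheduled contact from 7 to 30 − 7 = 23 days. That is true. Section 10.1.7 already accepts spontaneous reporting to day 30, and the fault here is a rule that names a contact that does not exist, not the use of spontaneous reporting.

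**Conclusion.** The point holds, at minor severity. Section 17.8.1 ties the end of SAE reporting to a contact at 11 to 17 days, while the only scheduled call falls 4 to 10 days after a Day 112 last dose. Read with its own limit, it also makes eCRF entry optional for SAEs on nominal days 15 to 30 (16 days), a period in which Sections 7.1 and 10.1.7 still require follow-up and reporting. Sites may record the same late SAE differently.

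This rests on the last dose falling at the end of treatment visit and on reading the follow-up window as the 2 weeks in Section 17.8.1. The documents give no SAE rate for these days, so no number of affected events can be stated.

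It would be wrong to infer that SAEs go unreported, that the arms are treated differently, or that the safety comparison is biased. Known SAEs reach the CRO on any reading, the rule is the same in both arms, and efficacy, power and alpha are not touched.

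**What to change.** Amend Section 17.8.1 as follows:
- Make SAEs reportable from informed consent until 30 days after the last dose. State that they are asked about at the scheduled 1-week call (Day 119 ±3) and collected by spontaneous report after that.
- Delete the reference to a contact at 2 weeks. Simply putting the 1-week call in its place would end reportability at day 7 beside a 30-day window, so the sentence has to be rewritten.
- Define the follow-up window as these 30 days, in line with Sections 7.1 and 10.1.7, counted by the date the SAE occurs. Section 7.1 already counts by occurrence; Section 10.1.7 counts by report and should be aligned.
- Require eCRF entry of every SAE the investigator learns of that occurred within the window.

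No visit, call or patient burden is added. The eCRF must stay open for SAE entry for about 30 − 7 = 23 days after the last patient's call. The Summary plans last patient out on 30 November 2020 and the study report on 31 March 2021, which is 31 + 31 + 28 + 31 = 121 days, so there is room for this.

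The alternative is to keep 2 weeks and schedule a contact at nominal Day 112 + 14 = 126 (±3). That costs an extra call per patient and still leaves days 15 to 30 to be settled.
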